Standard preventive care. If on the seventh day after randomization the patient is still hospitalized, after the inspection of the skin, the CRF is closed and the study concluded.

Standard preventive care

Evaluation of the risk of developingPD with a Braden scale within 24 hours of admission. Positioning of the patient on a preventive or curative anti-decubitus mattress (static or alternating pressure) if Braden value ≤ 16 or in any case according to the hospital policy, daily inspection of the skin and mobilization of the patient at least every 4 hours (in the surgical patient at least in the post-operative period) if the clinical conditions allow it (NPUAP 2014). Management of incontinence, humidity control and prevention of skin maceration and rubbing / friction during postural changes as per hospital policy.

Method

At the entrance of the patient in the ward, the nurse dedicated to the first reception assesses whether the person has the necessary criteria to be enrolled in the study. In the positive case, he/she will explain to the patient or to his legal guardian, the rationale of the study, he/she will submit the information requesting consent to the participation granting the necessary time for reading and consultation before any consent and signature. If the patient consents, the nurse has the consent signed and attached to the medical record by setting the first part of the CRF (attachment). If the patient at risk refuses the participation, if he/she has other exclusion criteria or if it is not possible to collect the consent, the nurse transcribes it on the CRF and files it. If the patient agrees to participate in the study, the dedicated nurse proceeds to randomization (see below for methods) taking the first opaque envelope according to the external progressive number. It transcribes in the CRF the date, the patient's ID, if he already has PD not to the sacrum and their category and location. It also sign the study arm and other variables of interest. If the patient is in the experimental arm, the nurse, in addition to the standard preventive care, applies the MSP to the sacrum and writes date and time on the CRF and on the MPS. However, the foam must be applied within 24 hours of admission. If this

time interval is exceeded, the researcher will mark the problem in CRF in the "NOTES" part and the patient leaves the study and the CRF is archived.

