- At discharge or on the appearance of pressure lesion on the sacrum ≥ 2nd category, the CRF is closed and the patient ends the study. If the patient has developed PD the treatment of the lesion will be performed according to the hospital policy.
- The medication will be removed, however, no later than the first 7 days of admission after which the patient ends the study.

Study exit criteria

- Withdrawal of informed consent before randomization
- Not randomized within 24 hours of admission

Conclusion of the study in the single recruited subject

- Withdrawal of consent after randomization
- The appearance of irritation to the skin caused by the dressing. The dressing is removed, reported in CRF and irritation treated as per hospital policy.
- At the request of the patient due to discomfort due to preventive medication.
- On discharge / death / transfer to ward not involved in the study before the 7th day after randomization
- After 7 days from randomization in the absence of PD to the sacrum
- The appearance of pressure injury to the sacrum higher than the first category

Sample size

From a randomized monocentric study of at-risk patients with a hip fracture where polyurethane foams were used in prevention, the incidence in the experimental group was 4.5% while in the control group of 15.4%. Similar deltas had also been identified in other trials in intensive care patients. Assuming similar results in the population subject of the present study and taking into account an alpha error of 0.05 and a beta error of 20%, it is necessary to enroll at least 228 patients at risk. In order to allow analyzes by subgroup (see the "statistical analysis" section) the sample size must be guaranteed for each area (medical, surgical, intensive).

Taking into account also a possible loss at the follow-up of 10% and also assuming a 10% withdrawal rate, the necessary sample will be 280 patients per area and therefore a total of 840 patients (420 per arm). Each hospital involved will enroll 40 patients per area involved in that specific hospital.

Randomization

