At the Research Center for Health Professions of the Rizzoli Orthopedic Institute in Bologna (coordinating center), using the site: www.randomization.com, a randomization list will be generated in blocks of 10. A sequence of opaque envelopes will be prepared with outside a progressive number. Inside the envelope a label will be placed that will contain the words "yes" or "no", according to the sequence indicated by the generated list.

The envelopes will always be sealed at the Research Center and the list kept under lock and key. The envelopes will be placed in a dedicated box and delivered to the nursing research manager of the hospitals involved in the study. In each ward/area a reference nurse will be identified and 40 envelopes delivered.

Statistical analysis

The analysis of the results will be carried out for Intention to Treat.

All continuous data will be expressed in terms of average and standard deviation. One Way ANOVA will be used to evaluate the differences between the averages of the experimental and comparison group. If the Levene test for homogeneity of variance were significant (p <0.05), the Mann Whitney test will be used. For all dichotomous variables the incidence, relative risk, relative risk reduction and number needed to treat will be calculated. The exact

Fisher test will be used to evaluate the differences between the incidences of different outcomes between the experimental group and the control group.

Subgroup analysis:

- by area of belonging (medical, surgical or intensive)
- by risk level according to the Braden classification: Severe (total score 9); High Risk (10-12) Moderate Risk (13-14); low Risk (15-16). (Pancorbo-Hidalgo PL 2006)
- by origin (domicile vs. other settings)

For all tests, a p <0.05 will be considered significant.

The statistical analysis will be done using the "Statistical Package for the Social Sciences" (SPSS) software version 15.0 (SPSS Inc., Chicago, USA)

Possible deviations from the protocol and / or critical issues and related behavior to be followed in all situations

- If the dedicated nurse, during the daily inspection, realizes that the sacral MSP (in the patients of the experimental arm) has been removed without being positioned anymore, he provides to reposition it, marking in the CRF that the patient for that day remained without.

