- If instead the MSP is present and the patient belongs to the control group, the dedicated nurse reports the violation of the CRF randomization but leaves the MSP and treats the patient as reported for the experimental group. At the analysis of the results, if these violations have occurred, we will proceed in addition to the analysis for Intention to Treat also for Protocol.
- If the patient is replaced by a different MSP (different brand) than the one in the studio, the dedicated nurse replaces it and marks the problem in CRF.

Safety / risk assessments for participants:

Patients are treated according to protocols and policy already in place (prevention and treatment of pressure injuries), and always in strict compliance with the Good Clinical Practice (GCP), there are no additional risks for the participants. The patient who eventually develops pressure ulcer will be treated as per hospital policy. If the patient develops a category I sacral lesion remains in the study. The event is marked in the data collection form (CRF). The rationale for this permanence involves both the difficulty in the differential diagnosis with skin redness (Sterner 2011) and the need to detect the secondary outcome

"Incidence of PD to the sacred category \geq II ° according to the NPUAP scale". The treatment of a category I injury involves the use of creams or at the most of ultrathin advanced dressing. If used in the control group patient it will be reported in CRF. If the patient belongs to the experimental group, no additional action is necessary.

Duration of the study

The project lasts a total of 12 months which includes the training of the staff of the centers involved, the recruitment of patients, the collection and processing of data. The time per patient is 7 days or until discharge if it occurs before the seventh day of admission. The date of the start of the trial will be considered to be the approval of the Ethics Committee for each center.

The timing of the study includes the following subdivision:

- Months 1 training of the centers involved
- Months 2- 6- patient enrollment and database implementation
- Months 7-12 Data analysis and results dissemination

Ethical and Administrative Aspects

Informed consent

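### A control patient found with the foam keeps it and is managed as experimental, while the opposite departure is corrected; the resulting one-way crossover dilutes the intention-to-treat difference and is answered only by an undefined per-protocol analysis

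*Combined protocol and SAP*

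**What the plan says.** The Comparison section gives the control arm standard care, with follow-up to day 7: "Standard preventive care. If on the seventh day after randomization the patient is still hospitalized". The foam is the addition that defines the experimental arm (Intervention).

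The section on possible deviations then treats the two kinds of departure differently.

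- Dressing-arm patient found without the foam: the nurse restores the allocation, "he provides to reposition it, marking in the CRF that the patient for that day remained without".
- Control patient found with the foam: the nurse reports the violation but "leaves the MSP and treats the patient as reported for the experimental group".

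For the analysis, the Statistical analysis section states: "The analysis of the results will be carried out for Intention to Treat". The deviations section adds that "if these violations have occurred, we will proceed in addition to the analysis for Intention to Treat also for Protocol". No section defines the per-protocol population or says whether a crossed-over control is excluded or counted as a dressing patient.

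A dressing-arm patient who stops because of discomfort leaves the study; the list of individual study endings includes "At the request of the patient due to discomfort due to preventive medication". Among patients still followed, sustained crossover can therefore run only from control to dressing.

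**The concern.** The two arms are handled on different principles. In one arm the departure is ended and the day noted; in the other it continues by instruction for the rest of follow-up. The contrast the trial sets out to estimate, foam plus standard care against standard care, weakens with every control handled this way.

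Two things are at stake. First, the ITT difference shrinks, and the Sample size section allows for loss to follow-up and withdrawal but not for crossover. This matters most within areas, because that section requires the full sample size in each of the three. Second, the plan's only response is a comparison of groups no longer formed by randomisation. Ward staff are not blinded, so which controls receive a foam may depend on perceived risk. If it does, removing or reclassifying them biases the comparison even when the dressing does nothing.

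**Working it through.** **Inputs from the Sample size section.** The source trial's rates: "the incidence in the experimental group was 4.5% while in the control group of 15.4" per cent. Alpha is 0.05 and power 80%; 228 evaluable patients and 280 enrolled per area; 840 in total. Sidedness is not stated; two-sided is assumed because it reproduces the plan's figure. **Assumed:** the share c of controls who keep the foam, and their risk.

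**The plan's own figure.** Unpooled normal formula: n per arm = (0.154×0.846 + 0.045×0.955)×(1.960 + 0.842)² / 0.109² = 114.5, or 228.9 in total, against 228 stated. Inflation: 228/(0.9×0.9) = 281.5, against 280 stated. Both reproduce within rounding.

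**ITT, average-risk crossover.** Control risk = 0.154 − c×0.109. Power = Φ(difference/SE − 1.96), with unpooled SE. Full benefit is assumed from the start, so for a given c this is an upper bound on dilution by average-risk patients.

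| c | Control incidence | Difference (points) | Power, one area (114 per arm) | Power, pooled (342 per arm) | Evaluable N per area for 80% |
|---|---|---|---|---|---|
| 0% | 15.4% | 10.9 | 80% | 99.8% | 229 |
| 5% | 14.9% | 10.4 | 77% | 99.6% | 248 |
| 10% | 14.3% | 9.8 | 73% | 99.4% | 270 |
| 20% | 13.2% | 8.7 | 65% | 98.2% | 326 |

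With the planned Fisher exact test at 114 per arm, power is 74, 70, 66 and 56% at the same four rates. The pooled column uses 3 × 114 = 342 evaluable per arm.

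If the dressing has no effect, crossed-over controls have the risk they would have had anyway. The ITT difference stays at zero and type I error is not inflated.

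**Per-protocol, no dressing effect.** Suppose 10% of controls cross over with twice the average risk (30.8%).

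- Remaining controls: (0.154 − 0.1×0.308)/0.9 = 0.137.
- Crossovers excluded: RR = 0.154/0.1369 = 1.13.
- Crossovers counted as dressing patients: that arm's risk = (0.154 + 0.1×0.308)/1.1 = 0.168; RR = 0.168/0.1369 = 1.23.

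If instead they carry half the average risk (7.7%), the remaining controls are at (0.154 − 0.0077)/0.9 = 0.1626. The RR is 0.154/0.1626 = 0.95 by exclusion, and [(0.154 + 0.0077)/1.1]/0.1626 = 0.90 by reassignment. An inert dressing can look harmful or helpful, depending on who crosses over.

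**Planned effect, 10% crossing over at twice the average risk.** Let crossovers take the source trial's relative risk, 4.5/15.4 = 0.292.

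- ITT: control = 0.1232 + 0.1×0.308×0.292 = 0.132; difference 8.7 points.
- Per-protocol by exclusion: 13.7 − 4.5 = 9.2 points.
- Per-protocol by reassignment: 13.69 − (0.045 + 0.0090)/1.1×100 = 13.69 − 4.91 = 8.8 points.
- Complier-adjusted (ITT difference divided by the between-arm difference in the proportion receiving foam, here 1 − 0.1): 8.72/0.9 = 9.7 points. This equals the true effect among compliers: 13.69×(1 − 0.292) = 9.7.

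**Limits of the complier-adjusted estimate.** With average-risk crossovers and full benefit it returns 9.81/0.9 = 10.9. If 10% of controls cross over and get only half the benefit, the ITT difference is 10.9 − 0.1×5.45 = 10.36 and the estimate is 10.36/0.9 = 11.5, an over-correction. Its standard error is about the ITT standard error divided by 0.9, so roughly 11% larger.

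**The case against.** Much of the case on the other side stands.

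- **The overall comparison is safe at these rates.** Pooled power is 98% or more up to 20% crossover. A reader might infer that the rule threatens the trial's main result; the plan's own numbers do not support that. The loss concerns the comparisons by area.
- **Rate and selection are assumed.** A reader might infer that nurses will give foam to the highest-risk controls, so that both analyses lean towards a false finding of no benefit. The documents do not say who would receive foam by mistake. If misapplication is unrelated to risk, excluding these patients leaves the estimate unbiased; if lower-risk controls receive it, the per-protocol bias reverses. Only the ITT dilution has a fixed direction, provided the dressing works.
- **The control rule is an explicit contingency with its own analysis.** It departs from the allocated comparator, but it is not a slip of drafting, and the documents give no ground for calling it clinically wrong.
- **Part of the safeguard exists.** ITT by allocated arm is already planned and the violation is already reported in the CRF. What is missing is an explicit record of duration.
- **The complier-adjusted estimate is no cure.** In the selective example it gives 9.7 points rather than 10.9, only 0.5 more than exclusion, and it over-corrects under partial exposure.

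None of this removes the unequal handling of the arms, the missing per-protocol definition, or that analysis's exposure to bias when there is no effect. The complier-adjusted estimate is zero in expectation in that case, which is its main advantage.

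**Conclusion.** The point holds in a limited form and merits a change to the plan. As written, the protocol ends one kind of departure and sustains the other, and the analysis it adds in response is neither defined nor protected by randomisation.

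The cost to ITT is conditional on a crossover rate the documents do not give. In one area, every 10% of average-risk controls who keep the foam removes about 1.1 points from the planned difference, and the first 10% takes power from 80% to about 73%. The per-protocol distortion depends on who crosses over: with 10% crossing over and no dressing effect, the RR runs from 0.90 (half the average risk, reassigned) to 1.23 (twice the average risk, reassigned). These figures rest on the source trial's rates, a two-sided test and, for ITT, full benefit in every crossover. They do not show that the overall conclusion will be wrong.

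**What to change.** The sponsor should reconcile the Comparison section with the two deviation rules, so that departures from allocation follow one stated principle in both arms. Which bedside rule applies is the sponsor's decision and is not proposed here.

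Whatever is chosen:

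1. Record in the CRF, for each control patient found with the foam, the day it was found and the days it was in place.
2. Report crossover by arm and area.
3. Keep the ITT analysis by allocated arm, as already planned.
4. Pre-specify a complier-adjusted (instrumental-variable) estimate as the supplementary analysis for these violations. State that it targets compliers, and report it with the days of exposure because a yes/no exposure over-corrects when exposure is partial.
5. If a per-protocol analysis is kept, define its population, including how crossed-over controls are classified, and label it a non-randomised comparison.

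The cost is one reconciled paragraph, a short CRF entry and one additional analysis. The complier-adjusted interval will be wider than the ITT interval. No change to the sample size is needed for the pooled comparison at the rates examined.
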